17.4.2.2 Safety endpoints

In terms of AEs, as a minimum, SAEs will be tabulated separately using the in-trial observation period.

All events in the in-trial observation period will be listed with information about whether it appeared in the on-treatment observation period or not.

Number of treatment emergent adverse events

Adverse events (AEs) will be coded using the Medical Dictionary for Regulatory Activities (MedDRA). AEs will be presented based on system organ class and preferred terms.

A Treatment Emergent Adverse Event (TEAE) is defined as an event that has an onset date on or after the first day of exposure to randomised treatment, and no later than seven days after the last day of exposure to randomised treatment.

TEAEs are summarised descriptively, whereas AEs not defined as treatment emergent are presented in listings, including AEs reported in the 30-day follow-up period. The summaries of TEAEs are made displaying the number of subjects with at least one event, the percentage of subjects with at least one event, the number of events and the event rate per 100 patient years of exposure. These summaries are done by seriousness, severity, relation to insulin treatment, relation to technical complaint, premature treatment discontinuation due to AEs, AEs leading to withdrawal from trial and outcome.

Furthermore, summary tables based on system organ class and preferred terms are made for:

- All TEAEs
- Serious TEAEs
- Possibly and probably related TEAEs
- Severe TEAEs
- TEAEs with preferred term that are experienced by at least 5% of the subjects in any treatment arm or by at least 5% of all subjects

For AEs where additional information is recorded, this will be listed.

AEs occurring during the run-in period are considered non-treatment emergent and will be summarised separately.

Number of treatment emergent injection site reactions

Treatment emergent injection site reactions occurring during the trial will be summarised and listed.

Classification of Hypoglycaemia

Treatment emergent: hypoglycaemic episodes will be defined as treatment emergent if the onset of the episode occurs on or after the first day of exposure to randomised treatment, and no later than one day after the last day of exposure to randomised treatment.

Nocturnal hypoglycaemic episodes: episodes occurring between 00:01 and 05.59 both inclusive.

Hypoglycaemic episodes are classified according to the Novo Nordisk classification of hypoglycaemia (see Figure 17–1) and the ADA classification of hypoglycaemia (see Figure 17–2).

[figure not shown]
Novo Nordisk classification of hypoglycaemia

In normal physiology, symptoms of hypoglycaemia occur below a PG level of 3.1 mmol/L (56 mg/dL). Therefore, Novo Nordisk has included hypoglycaemia with PG levels below this cut-off point in the definition of BG confirmed hypoglycaemia.

Novo Nordisk uses the following classification (see Figure 17–1) in addition to the ADA classification:

Protocol		Date:	23 February 2018	Novo Nordisk
Trial ID: NN1218-4113	CONFIDENTIAL	Version:	4.0	
UTN: U1111-1180-0636	CONFIDENTIAL	Status:	Final	
EudraCT no.: 2016-000878-38		Page:	93 of 112	

- Severe hypoglycaemia according to the ADA classification. 34
- Severe or BG confirmed hypoglycaemia: An episode that is severe according to the ADA classification 34 or BG confirmed by a PG value <3.1 mmol/L (56 mg/dL) with or without symptoms consistent with hypoglycaemia.

Note: Glucose measurements are performed with capillary blood calibrated to plasma equivalent glucose values

BG: blood glucose PG: plasma glucose SMPG: Self-measured plasma glucose

Figure 17-1 Novo Nordisk classification of hypoglycaemia

Protocol
Trial ID: NN1218-4113
UTN: U1111-1180-0636

Date: 23 February 2018 | Novo Nordisk
Version: 4.0
Status: Final

[figure not shown]
Page:

94 of 112

ADA classification ³⁴ of hypoglycaemia

EudraCT no.: 2016-000878-38

- Severe hypoglycaemia: An episode requiring assistance of another person to actively administer carbohydrate, glucagon, or take other corrective actions. Plasma glucose concentrations may not be available during an event, but neurological recovery following the return of PG to normal is considered sufficient evidence that the event was induced by a low PG concentration.
- Asymptomatic hypoglycaemia: An episode not accompanied by typical symptoms of hypoglycaemia, but with a measured PG concentration ≤ 3.9 mmol/L (70 mg/dL).
- Documented symptomatic hypoglycaemia: An episode during which typical symptoms of hypoglycaemia are accompanied by a measured PG concentration ≤ 3.9 mmol/L (70 mg/dL).
- Pseudo-hypoglycaemia: An episode during which the person with diabetes reports any of the typical symptoms of hypoglycaemia with a measured PG concentration > 3.9 mmol/L (70 mg/dL) but approaching that level.
- Probable symptomatic hypoglycaemia: An episode during which symptoms of hypoglycaemia are not accompanied by a PG determination but that was presumably caused by a PG concentration ≤ 3.9 mmol/L (70 mg/dL).

Note: Glucose measurements are performed with capillary blood calibrated to plasma equivalent glucose values PG: plasma glucose SMPG: Self-measured plasma glucose

Figure 17–2 ADA classification of hypoglycaemia

Protocol		Date:	23 February 2018	Novo Nordisk
Trial ID: NN1218-4113	CONFIDENTIAL	Version:	4.0	
UTN: U1111-1180-0636	CONFIDENTIAL	Status:	Final	
EudraCT no.: 2016-000878-38		Page:	95 of 112	

Treatment emergent hypoglycaemic episodes are presented in terms of the number of subjects with at least one event (N), the percentage of subjects with at least one event (%), the number of events (E) and the event rate per 100 years of exposure (R). Separate summaries are made by severity considering all episodes, nocturnal and daytime episodes using Novo Nordisk and ADA classified episodes. All episodes will also be summarised by category, including summaries in relation to time since start of meal, as occurring during1, 2, and 4 hours after start of meal, and from 2 hours (exclusive) to 4 hours (inclusive) after start of meal, respectively.

The number of treatment emergent severe or BG confirmed hypoglycaemic episodes (all, daytime, nocturnal, 1 hour, 2 hours, 4 hours and from 2 hours (exclusive) to 4 hours (inclusive) after start of the meal) will be analysed based on the FAS using a negative binomial regression model with a log-link function and the logarithm of the time period in which a hypoglycaemic episode is considered treatment emergent as offset. The model will include treatment, region and metformin use at baseline (Yes/No) as factors. To the extent where data allow, separate analysis will be performed for severe hypoglycaemic episodes.

Change from baseline in clinical evaluations 16 weeks after randomisation:

Physical examination

The physical examination parameters (head, ears, eyes, nose, throat, neck, respiratory system, cardiovascular system, gastrointestinal system incl. mouth, musculoskeletal system, central and peripheral nervous system, skin), and their change from baseline, will be summarised descriptively using the on-treatment period. All findings will be listed.

Vital signs

Vital signs include diastolic blood pressure, systolic blood pressure and pulse. The measurements will be summarised descriptively using the on-treatment period and both actual values as mean change and change from baseline.

Electrocardiogram

ECG findings will be summarised descriptively using the on-treatment period and including summaries of the change from baseline. Change from baseline will be summarised as normal/abnormal not clinically significant/abnormal clinically significant categorisation in shift tables.

Fundoscopy/fundus photography

Fundoscopy/fundus photography findings will be summarised descriptively using the on-treatment period and including summaries of the change from baseline. Change from baseline will be

Protocol		Date:	23 February 2018	Novo Nordisk
Trial ID: NN1218-4113	CONFIDENTIAL	Version:	4.0	
UTN: U1111-1180-0636		Status:	Final	
EudraCT no.: 2016-000878-38		Page:	96 of 112	

summarised as normal/abnormal not clinically significant/abnormal clinically significant categorisation in shift tables.

Change from baseline in clinical laboratory assessments 16 weeks after randomisation

Change from baseline 16 weeks after randomisation in central laboratory assessments:

- Haematology (erythrocytes, haematocrit, haemoglobin, leucocytes, thrombocytes)
- Biochemistry (ALT, AST, albumin, alkaline phosphatase, creatinine, potassium, sodium, total bilirubin)

Individual laboratory values will be compared to their relevant reference range (when existing) and flagged as being below or above the range. The measurements and their change from baseline will be summarised descriptively using the on-treatment period. Change from baseline will be summarised both the actual values and the low/normal/high categorisation in shift tables.

Change from baseline in body weight and body mass index 16 weeks after randomisation

The measurements will be summarised descriptively using the on-treatment period and the actual values as mean change.

Change from baseline in body weight will be analysed based on all planned post baseline measurements until or at 16 weeks after randomisation using a statistical model similar to 1) except with the corresponding baseline measurement as covariate.

Protocol
Trial ID: NN1218-4113

CONFIDENTIAL

Date: 23 February 2018 | Novo Nordisk
Version: 4.0

Status:

Page:

Final

97 of 112

UTN: U1111-1180-0636 EudraCT no.: 2016-000878-38

Ethics

18

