12.1 Definitions

12.1.1 Adverse event

An adverse event (AE) is any untoward medical occurrence in a subject administered a medicinal product, and which does not necessarily have a causal relationship with this treatment.

An AE can therefore be any unfavourable and unintended sign (including an abnormal laboratory finding), symptom or disease temporally associated with the use of a product, whether or not considered related to the product.

An AE includes:

- A clinically significant worsening of a concomitant illness.
- A clinical laboratory AE (CLAE): a clinical laboratory abnormality which is clinically significant, i.e. an abnormality that suggests a disease and/or organ toxicity and is of a severity that requires active management. Active management includes active treatment or further investigations, for example change of medicine dose or more frequent follow-up due to the abnormality.

The following should **not** be reported as AEs:

- Pre-existing conditions, including those found as a result of screening or other trial
 procedures performed before exposure to trial product (pre-existing conditions should be
 reported as medical history or concomitant illness).
- Pre-planned procedures unless the condition for which the procedure was planned has
 worsened from the first trial related activity after the subject has signed the informed
 consent.
- Non-serious hypoglycaemia is an AE, but is reported on a hypoglycaemic episode form instead of on an AE form, see Section 8.4.2.

The following three definitions are used when assessing an AE:

- Severity
- Mild no or transient symptoms, no interference with the subject's daily activities.
- Moderate marked symptoms, moderate interference with the subject's daily activities.
- Severe considerable interference with the subject's daily activities; unacceptable.
- Causality

Relationship between an AE and the relevant trial product(s):

- Probable Good reason and sufficient documentation to assume a causal relationship.
- Possible A causal relationship is conceivable and cannot be dismissed.
- Unlikely The event is most likely related to aetiology other than the trial product.

Page:

64 of 112

• Final outcome

EudraCT no.: 2016-000878-38

- Recovered/resolved The subject has fully recovered, or by medical or surgical treatment
 the condition has returned to the level observed at the first trial-related activity after the
 subject signed the informed consent.

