12.2 Reporting of adverse events

All events meeting the definition of an AE must be collected and reported. This includes events from the first trial-related activity after the subject has signed the informed consent until the end of the post-treatment follow-up period (FU2). For subjects discontinuing trial products prematurely this also includes events after the post-treatment follow-up period until the last contact (Visit 30). The events must be recorded in the applicable eCRF forms in a timely manner, see timelines below and Figure 12–1.

During each contact with the trial site staff, the subject must be asked about AEs and technical complaints, for example by asking: "Have you experienced any problems since the last contact?"

All AEs, either observed by the investigator or subject, must be reported by the investigator and evaluated.

All AEs must be recorded by the investigator on an AE form. The investigator should report the diagnosis, if available. If no diagnosis is available, the investigator should record each sign and symptom as individual AEs using separate AE forms.

For SAEs, a safety information form must be completed in addition to the AE form. If several symptoms or diagnoses occur as part of the same clinical picture, one safety information form can be used to describe all the SAEs.

Protocol		Date:	23 February 2018	Novo Nordisk
Trial ID: NN1218-4113	CONFIDENTIAL	Version:	4.0	
UTN: U1111-1180-0636	CONFIDENTIAL	Status:	Final	
EudraCT no.: 2016-000878-38		Page:	67 of 112	

For all non-serious AEs, the applicable forms should be signed when the event is resolved or at the end of the trial at the latest.

Timelines for initial reporting of AEs:

[figure not shown]
The investigator must complete the following forms in the eCRF within the specified timelines:

• **SAEs:** The AE form **within 24 hours** and the safety information form **within 5 calendar** days of the investigator's first knowledge of the SAE. Both forms must be signed within 7 calendar days from the date the information was entered in the eCRF.

For SAEs requiring reporting on a specific event form: In addition to the above the specific event form within **14 calendar days** from the investigator's first knowledge of the AE.

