12.3 Follow-up of adverse events

The investigator must record follow-up information by updating the forms in the eCRF.

Follow-up information must be reported to Novo Nordisk according to the following:

• SAEs: All SAEs must be followed until the outcome of the event is "recovered/resolved", "recovered/resolved with sequelae" or "fatal", and until all queries have been resolved. Cases of chronic conditions, cancer or AEs ongoing at time of death (where death is due to another AE) may be closed with the outcome "recovering/resolving" or "not recovered/not resolved". Cases can be closed with the outcome of "recovering/resolving" when the subject has completed the follow-up period and is expected by the investigator to recover.

The SAE follow-up information should only include new (e.g. corrections or additional) information and must be reported **within 24 hours** of the investigator's first knowledge of the

 Protocol
 Date:
 23 February 2018
 Novo Nordisk

 Trial ID: NN1218-4113
 Version:
 4.0

 UTN: U1111-1180-0636
 Status:
 Final

Page:

69 of 112

information. This is also the case for previously non-serious AEs which subsequently become SAEs.

• Non-serious AEs: Non-serious AEs must be followed until the outcome of the event is "recovering/resolving", "recovered/resolved" or "recovered/resolved with sequelae" or until the end of the follow-up period stated in the protocol, whichever comes first, and until all queries related to these AEs have been resolved. Cases of chronic conditions, cancer or AEs ongoing at time of death (where death is due to another AE) may be closed with the outcome "recovering/resolving" or "not recovered/not resolved". Cases can be closed with the outcome of "recovering/resolving" when the subject has completed the follow -up period and is expected by the investigator to recover.

The investigator must ensure that the recording of the worst case severity and seriousness of an event is kept throughout the trial. A worsening of an unresolved AE must be reported as follow up with re-assessment of severity and/or seriousness of the event.

Queries or follow-up requests from Novo Nordisk must be responded to **within 14 calendar days** from the date of receipt of the request, unless otherwise specified in the follow-up request.

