2.4.2.2 Safety endpoints

In terms of AEs, as a minimum, SAEs will be tabulated separately using the in-trial observation period.

All events in the in-trial observation period will be listed with information about whether it appeared in the on-treatment observation period or not.

Number of treatment emergent adverse events

Adverse events (AEs) will be coded using the Medical Dictionary for Regulatory Activities (MedDRA). AEs will be presented based on system organ class and preferred terms.

A Treatment Emergent Adverse Event (TEAE) is defined as an event that has an onset date on or after the first day of exposure to randomised treatment, and no later than seven days after the last day of exposure to randomised treatment.

TEAEs are summarised descriptively, whereas AEs not defined as treatment emergent are presented in listings, including AEs reported in the 30-day follow-up period. The summaries of TEAEs are made displaying the number of subjects with at least one event, the percentage of subjects with at least one event, the number of events and the event rate per 100 patient years of exposure. These summaries are done by seriousness, severity, relation to insulin treatment, relation to technical complaint, premature treatment discontinuation due to AEs, and outcome.

Furthermore, summary tables based on system organ class and preferred terms are made for:

All TEAEs

- Serious TEAEs
- Possibly or probably related TEAEs
- Severe TEAEs
- TEAEs with preferred term that are experienced by at least 5% of the subjects in any treatment arm or by at least 5% of all subjects

For AEs where additional information is recorded, this will be listed.

AEs occurring during the run-in period are considered non-treatment emergent and will be summarised separately.

Number of treatment emergent injection site reactions

Treatment emergent injection site reactions occurring during the trial will be summarised and listed.

Classification of Hypoglycaemia

Treatment emergent: hypoglycaemic episodes will be defined as treatment emergent if the onset of the episode occurs on or after the first day of exposure to randomised treatment, and no later than one day after the last day of exposure to randomised treatment.

Nocturnal hypoglycaemic episodes: episodes occurring between 00:01 and 05.59 both inclusive.

[figure not shown]

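### Treatment emergence is decided by onset date alone, while worsening of an open AE is filed under the old record, so a run-in AE that becomes more severe or serious on randomised insulin drops out of the TEAE tables

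*Protocol*

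**What the plan says.** The classification rule is in Protocol version 4.0, section 17.4.2.2. A TEAE "is defined as an event that has an onset date on or after the first day of exposure to randomised treatment", and the window closes "no later than seven days after the last day of exposure to randomised treatment". SAP 2.4.2.2 has the same rule: "A Treatment Emergent Adverse Event (TEAE) is defined as an event that has an onset date on or after the first day of exposure". Neither text has a clause for an event that begins earlier and then changes in severity or seriousness. Both declare run-in AEs non-treatment emergent, to be summarised separately, and make no exception for later worsening. SAP section 3 lists changes to the AE summaries, but the TEAE definition is not among them.

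The recording rule is in Protocol 12.3: "A worsening of an unresolved AE must be reported as follow up with re-assessment of severity and/or seriousness of the event". The same section says "The investigator must ensure that the recording of the worst case severity and seriousness of an event is kept throughout the trial". On the SAE follow-up route, which requires reporting within 24 hours, it adds "This is also the case for previously non-serious AEs which subsequently become SAEs".

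Collection begins at consent, under Protocol 12.2: "This includes events from the first trial-related activity after the subject has signed the informed consent". Protocol 12.1.1, by contrast, lists as an AE in its own right: "A clinically significant worsening of a concomitant illness".

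**The concern.** Each rule is ordinary when read alone. The difficulty is how they combine in a trial with a long pre-randomisation phase. AEs are collected through about 2 weeks of screening and 12 weeks of run-in before anyone takes blinded bolus insulin, so some will be open at Visit 14. If one of them worsens afterwards, the recording rule gives it no new onset date, and the classification rule looks at nothing else.

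Comparing safety is a stated secondary objective, and the number of TEAEs is a listed safety endpoint. The tables most read for harm by arm (All, Severe and Serious TEAEs) would omit some harm that appears on randomised treatment. The run-in table could carry grades that did not exist during the run-in.

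**Working it through.** The plan states no figure to reproduce. The check is a reading of the rules against one another.

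**One event followed through the rules.** Suppose an AE starts as mild in week -8, is open at Visit 14, and becomes severe or serious in week 6.

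1. It is collected, because collection starts at consent (12.2).
2. The week 6 change is follow-up on the same record, not a new AE (12.3). Retention of the original onset date is implied by this; the section does not say so in words.
3. The record now carries the worst grade reached (12.3).
4. Onset precedes the first randomised dose, so it is not a TEAE (17.4.2.2; SAP 2.4.2.2).
5. It is therefore absent from the All, Severe and Serious TEAE tables.
6. It belongs to the run-in summary. Neither document says which severity that summary uses. If it takes the value on the record, it shows a grade from week 6.

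**Three conditions that worsen in week 6, side by side.**

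| Condition | Governing text | Can the worsening be a TEAE? |
|---|---|---|
| Concomitant illness: present at Visit 1, or found by a trial procedure before trial product (8.2.4) | 12.1.1, 8.2.4: clinically significant worsening is its own AE | Yes |
| AE that arose in the run-in and is unresolved | 12.3: follow-up on the same record | No |
| Abnormal examination finding, such as ECG or eye | 8.4: clinically significant worsening from baseline is reported as an AE, with no word on new record or follow-up | Unclear |

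So similar worsening is classified differently according to when and how the condition first came to light.

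**Extent in time.** The first trial product is insulin degludec at Visit 2 (8.1.2). Conditions that trial procedures uncover before then count as concomitant illness and are covered. What remains is mainly AEs from the 12-week run-in, with some events arising in screening.

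**Size.** The documents give no count of run-in AEs, of AEs open at Visit 14, or of AEs that worsen later, so the undercount cannot be derived. To show the scale only, under an assumed share of randomised subjects with such an event:

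- 0.5%: 1072 × 0.005 = 5.4, about 5 subjects
- 2%: 1072 × 0.02 = 21.4, about 21 subjects

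Nothing in the documents supports either percentage.

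**The case against.** The strongest reply is that these events are mislabelled rather than lost. ECG, fundoscopy and laboratory results are summarised in shift tables from baseline, and physical examination is summarised as change from baseline with all findings listed. None of that depends on TEAE status. Non-emergent AEs are listed. SAEs are tabulated over the in-trial period, a change to serious must be reported within 24 hours, and an internal safety committee performs ongoing surveillance. Hypoglycaemia, the main risk of insulin, is counted per episode, and non-serious episodes go on their own form, so they largely escape the problem. The rule is the same in both double-blind arms, the AE summaries are descriptive, and no confirmatory test uses them.

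Most of this stands, and it rules out several stronger readings that a reader might infer:

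- **That no difference between arms in worsening could be seen.** The shift tables and listings show some of it.
- **That such worsening can never be a TEAE.** Section 8.4 can be read as calling for a new AE when an examination finding worsens from baseline, and 4.2 sets baseline at Visit 14. No text gives 12.3 precedence over 8.4.
- **That everything first seen between consent and Visit 14 is affected.** The definition of concomitant illness in 8.2.4 removes part of it.
- **That the share of calendar time before randomisation measures the loss.** Most AEs that begin before randomisation are correctly non-emergent.

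The reply does not close the gap. Listings are not a comparison by arm. The in-trial period starts at randomisation, and neither document says whether an AE with run-in onset that later turns serious enters the SAE table. That table would in any case miss AEs that become severe without being serious.

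**Conclusion.** The point holds for AEs already recorded before the first randomised dose, mainly in the run-in, that are unresolved at Visit 14 and then increase in severity or become serious. Followed as written, the plan leaves them out of all three main TEAE tables, and the run-in summary may show severity or seriousness reached only after randomisation.

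The conclusion rests on one inference: that follow-up on an existing record keeps its onset date. The size is unknown. The likely effect is an undercount of severe and serious TEAEs in both arms and possible dilution of a difference between them. The primary HbA1c analysis and the hierarchical tests are not touched. This is a gap worth closing because it is structural and cheap to repair, but it does not threaten the trial's main conclusion.

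**What to change.** Choose one of two routes. Using both could count the same worsening twice, once through the old record and once through a new one.

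- **Route A, definition.** In Protocol 17.4.2.2 and SAP 2.4.2.2, also count as treatment emergent any AE with onset before the first randomised dose whose severity increases, or which becomes serious, within the existing TEAE window. Capture the date of that change.
- **Route B, recording.** In Protocol 12.3, have worsening after the first randomised dose of an earlier-onset AE entered as a new AE, with onset at the date of worsening. This matches the treatment of concomitant illness.

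Under either route, reconcile 8.4 with 12.3 so that sites know whether worsening of an examination finding is a new AE or follow-up. State that the run-in summary uses severity and seriousness as they stood before randomisation.

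If recording can no longer be changed, the eCRF audit trail (Protocol 13.1) keeps old and new values with the date and time of entry. A supportive table by arm of such events could be built from it, on the understanding that the entry date is not necessarily the date of worsening.

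The cost is a sentence or two in the chosen section, slightly higher TEAE counts and minor data handling.
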